Laboratory examination	X		X	X	X		X	
Standard electrocardiogram	X		X	X	X	X	X	
Holter					X	X	X	
AFEQT scale	X			X	X	X	X	
Echocardiogram	X		X	X		X	X	
Medication status	X	X	X	X	X	X	X	
Adverse events	X	X	X	X	X	X	X	

Note: m=month; d=day; h=hour.

(1) **V1 Screening period:** If the patient has undergone relevant examinations before signing the informed consent form and within 14 days before surgery, these data can be collected as data for this clinical trial. Patients do not need to undergo relevant examinations, such as laboratory tests, electrocardiograms, etc.

(2) **General information:** date of birth, gender, height, weight.

(3) **Vital signs:** body temperature, blood pressure, heart rate/pulse.

(4) **Medical history:** including hypertension, diabetes, coronary heart disease, stroke, allergies, surgical history, etc.

5) Pregnancy test: urine/blood pregnancy test (only for premenopausal women, only before surgery).

(6) Laboratory examination (V6 only measures NT-proBNP, and all other visits involving laboratory examinations (such as V1, V3 and V4) must complete all the following examination items):

Routine blood test: red blood cells (RBC), white blood cells (WBC), hemoglobin (Hgb), platelets (PLT); Blood biochemistry: alanine aminotransferase/alanine aminotransferase (ALT), aspartate aminotransferase/aspartate aminotransferase (AST), total bilirubin (TBIL), direct bilirubin (DBIL), blood urea nitrogen/urea (BUN/CREA), creatinine (Cr), uric acid (UA); ESR; Electrolytes: potassium ion (K); Coagulation function: prothrombin time (PT), activated partial thromboplastin time (APTT), fibrinogen (FIB); C β -reactive protein; D-dimer; NT-proBNP; myocardial enzyme spectrum and high-sensitive cardiac troponin T: lactate dehydrogenase (LDH), creatine kinase isoenzyme (CK-MB), and high-sensitive cardiac troponin I (hs-cTnI);

(7) Long-term Holter: Use a single-lead 7-day long-term Holter for monitoring.

(8) Medication status: Record the medication used during the study period (from the signing of the informed consent to the end of the follow-up). Routine fluid preparation (normal saline, glucose solution), intraoperative anesthetics, and intraoperative anticoagulants do not need to be recorded. Medication used for corrective treatment of adverse events also needs to be recorded.

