3.2 Subject screening

Whether the selected patients meet the inclusion criteria requires the following assessments:

- (1) General information: age, gender, place of origin, contact information, etc.
- (2) Physical examination: height, weight; heart rate, blood pressure, etc.
- (3) Past medical history: hypertension, diabetes, coronary heart disease, cardiomyopathy, COPD, stroke, etc.; previous surgical history, including pacemaker implantation, thyroid disease history, etc.; previous medication history;
- (4) Electrocardiogram (including Holter);
- (5) Transthoracic echocardiogram (LVEF, LVEDD, LAD, e/e', etc.);
- (6) Transesophageal echocardiogram, MRI or CT examination of the left atrium and pulmonary veins;
- (7) Laboratory tests: routine blood tests, routine urine tests, routine stool tests, liver function tests, kidney function tests, electrolytes, blood sugar, blood lipids, myocardial markers, coagulation function tests, BNP or NT-proBNP, thyroid function tests, etc.
- (8) Informed consent was signed for the subjects who met the above requirements and agreed to participate in the study.

In this study, no examination items were included beyond those required for routine diagnosis and treatment.

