- (4) The incidence of AT/AF/AFL events 3 months later.;
- (5) Improvement of cardiac function 6 and 12 months after surgery, including echocardiogram E/e', proBNP, etc.

6. Methods and timing for evaluating, recording and analyzing safety parameters

- (1) Record the occurrence of death, stroke or transient ischemic attack of the subjects during the study;

(2) Surgical operation-related parameters (operation time, left atrial operation time, number of ablation discharges, X-ray exposure time and X-ray radiation, etc.) and intraoperative complications: Observe and record the occurrence of surgery-related adverse events from the beginning to the end of the surgery. All adverse events should be tracked and followed up until they return to normal or baseline, or are sufficient to explain the abnormality. If the subject's participation in this trial ends, it should be tracked until the last follow-up;

(3) Clinically significant vital signs and related examinations:

Vital signs: Vital signs should be checked during the screening period, 1, 2, 3, 6 and 12 months of outpatient follow-up, and observed and recorded;

Laboratory examination: blood routine, blood biochemistry, coagulation function, electrolytes, coagulation function, NT-proBNP, D-dimer, myocardial enzyme spectrum and high-sensitivity cardiac troponin I are performed during the follow-up period. When clinically significant abnormal laboratory test results are found, they should be re-examined and followed up until they return to normal or have no clinical significance or baseline status; relevant laboratory tests need to be completed before the patient is discharged;

Standard electrocardiogram: 12-lead surface electrocardiogram is performed during the screening period, 1, 3, 6 and 12 months of follow-up;

Holter is used for follow-up at 3, 6 and 12 months after surgery.

Echocardiogram: The investigator may choose to perform transthoracic echocardiogram or/and transesophageal echocardiogram according to the patient's condition;

AFEQT Atrial Fibrillation Patient Quality of Life Scale: The patient's quality of life is scored during the screening period and 1, 3, 6 and 12 months after surgery;

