(4) The occurrence of other adverse events and serious adverse events: Observe and record them throughout the trial. Serious adverse events should be tracked until the problem is resolved or the investigator determines that it has become "chronic" or "stable" or "sufficient to explain this abnormality". Reports of these adverse events should be recorded.

7. Safety evaluation

Safety refers to the absence of pulmonary vein stenosis, cardiac tamponade, phrenic nerve injury, esophageal injury, and femoral artery and vein injury, thrombosis/air embolism, myocardial infarction, stroke, TIA, asymptomatic cerebral infarction, coronary artery spasm, vagal reflex with severe bradycardia and other surgical complications during the perioperative period.

8. Time of participation in the study (each participation time and total time)

The time of participation in the study is the time when patients with persistent atrial fibrillation and HFpEF are planned to receive drug treatment or pulsed field ablation surgery, that is, the time of enrollment. The follow-up time is 1 month, 3 months, 6 months, and 12 months after enrollment. The total time is 12 months after the start of treatment. .

9. Data management and statistical analysis plan, data confidentiality plan

(1) The research data are managed and stored in the cardiology laboratory by full-time scientific research personnel.

(2) Data statistics and analysis

1. Statistical processing: SPSS22.0 statistical software was used for statistical analysis.
2. Normally distributed quantitative data, such as troponin, liver and kidney function, blood lipids, height, weight, EF, e/e', proBNP, etc.
3. Non-normally distributed quantitative data, such as age, are described as median ± interquartile range.
4. A t-test is planned for the results of molecular experimental data;
5. The composition ratio is used for statistical description of qualitative data, and the chi-square test is used for statistical inference. Cardiac function (NYHA classification) is tested using the K-W rank sum test;
6. $P < 0.05$ is considered significant.

10. Confidentiality Plan

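### Section 7 counts the absence of asymptomatic cerebral infarction and pulmonary vein stenosis as safety, but the first is never looked for and the second not systematically

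*Protocol*

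**What the plan says.** **The definition.** Protocol Section 7 (Safety evaluation) opens: "Safety refers to the absence of pulmonary vein stenosis, cardiac tamponade, phrenic nerve injury, esophageal injury". The list goes on to "thrombosis/air embolism, myocardial infarction, stroke, TIA, asymptomatic cerebral infarction, coronary artery spasm" and closes with "vagal reflex with severe bradycardia and other surgical complications during the perioperative period". Asymptomatic cerebral infarction is therefore a separate item from stroke and TIA.

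**The examinations.**
- Section 6, item (1), on neurological events: "Record the occurrence of death, stroke or transient ischemic attack of the subjects during the study". Silent infarction is not named and no brain imaging is mentioned.
- Section 6, item (3), on echocardiography: "The investigator may choose to perform transthoracic echocardiogram or/and transesophageal echocardiogram according to the patient's condition".
- Section 3.2, item (6), at screening: "Transesophageal echocardiogram, MRI or CT examination of the left atrium and pulmonary veins".
- Section 3.2, closing sentence: "In this study, no examination items were included beyond those required for routine diagnosis and treatment".
- The flow chart and the visit lists in Section 4.3 schedule echocardiography as the only imaging after treatment.
- The adverse-event notes to the flow chart and to Section 4.3 limit recording to events of clinical significance.
- Section 4.2.2, item (11), names pulmonary vein stenosis among the complications to record. It does not name silent infarction.

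**The concern.** A definition framed as absence works only if each component would be found when present. A silent infarct produces no symptom to prompt a test, so imaging is the only route to it, and none is planned. Under Section 7 as worded, a patient who was never examined for it is indistinguishable from one who was examined and found free of it.

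Safety is in the study title, perioperative safety is the first item of research content in Section 2.2, and complications form secondary endpoint (2). The Background also shows how zero counts tend to be read: it cites a study of the device with an unsafe-event rate of 0.7% and none of several named complications, pulmonary vein stenosis among them, and takes the low rate as proof of excellent safety. A zero for silent infarction here would invite the same reading with no ascertainment behind it. Both the definition and the schedule are fixed in the protocol, and no later analysis can recover events that were never ascertained.

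**Working it through.** The plan gives no rate or precision for these events, so there is no stated figure to reproduce. The check has two parts.

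**1. Each component against every place where data are collected**

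| Source in protocol | Asymptomatic cerebral infarction | Pulmonary vein stenosis |
|---|---|---|
| Section 3.2 (screening) | no brain imaging | transesophageal echo, MRI or CT |
| Flow chart, after treatment | no examination | echocardiogram at V3, V4, V6, V7; veins not specified |
| Section 4.3 visit lists | no examination | cardiac ultrasound; veins not specified |
| Section 4.2.2 (11), complications recorded | not named | named, no examination attached |
| Section 6 | only death, stroke or TIA recorded | transthoracic and/or transesophageal echo at the investigator's choice |
| Adverse-event notes | only if clinically significant | only if clinically significant |

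(The flow chart and Section 4.3 differ on whether an echo is done at 3 months. This does not change the result.)

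For silent infarction every cell is empty, so the probability of detection is zero apart from chance findings. For stenosis there is a route, but an optional one: symptoms, unscheduled imaging, or an echo that happens to show the veins.

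**2. What a zero count would be worth**

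Inputs: ablation group n = 79 (Section 3.1: 63 evaluable, 63 / (1 − 0.20) = 78.75, rounded up to 79). True rate p: not given in the documents; 5%, 10% and 20% are assumed for illustration only. Detection probability d: 0 if nobody looks, 1 if everyone is imaged; d = 0.10 is an assumed illustration of sporadic detection.

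Exact upper limit for 0 of n is 1 − α^(1/n):
- one-sided 95%: 1 − 0.05^(1/79) = 3.72%
- two-sided 95%: 1 − 0.025^(1/79) = 4.56%

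Expected cases seen = n × p × d. Probability of seeing none = (1 − p × d)^n.

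| Assumed p | Cases present (79 × p) | P(none seen), d = 1 | P(none seen), d = 0.10 | P(none seen), d = 0 |
|---|---|---|---|---|
| 5% | 3.95 | 0.017 | 0.67 | 1 |
| 10% | 7.9 | 0.0002 | 0.45 | 1 |
| 20% | 15.8 | <0.0001 | 0.20 | 1 |

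With complete imaging, zero of 79 would be strong evidence against a 5% rate. With none, zero is certain at every rate and carries no information, so the 3.7% or 4.6% limit would be spurious. The d = 0 column describes silent infarction as planned. The d = 0.10 column shows the kind of downward bias that applies to stenosis; its size cannot be derived from the protocol.

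**The case against.** The strongest reply is that Section 7 is a single descriptive sentence. It sets no composite rate, no patient-level classification as safe, no threshold and no confidence limit. The endpoint that will be analysed is secondary endpoint (2), and the protocol summary plans counts and frequencies of adverse events with an exact comparison between groups. Because only clinically significant events are recorded, the data will in effect be clinically apparent events anyway. That is fair as to consequences: no planned analysis yet claims that silent infarction was absent. It does not remove the mismatch, because Section 7 names the event and the rest of the protocol gives no means of finding it.

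Stronger conclusions are tempting, and the documents do not support them:
- **That stenosis cannot be detected after treatment.** Section 6 permits transesophageal echo, Section 3.2 lists that test among the examinations of the left atrium and pulmonary veins, and Section 4.2.2 (11) asks for stenosis to be recorded. Ascertainment is unsystematic, not impossible.
- **That the whole safety result will be near zero by construction.** Tamponade, stroke, TIA, vascular injury and similar events are clinically apparent and are captured. A low overall count could also arise honestly: at the 0.7% cited in the Background, the probability of no events in 79 is 0.993^79 = 0.57.
- **That centres which image more would be judged less safe.** No between-centre comparison of safety is planned; the by-centre summaries cover enrolment, completion and case distribution.

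One further point stands. Section 7 is confined to a perioperative period that it does not define, so a stenosis seen at a later visit might fall outside the definition. That adds to the under-counting of stenosis.

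**Conclusion.** The definition is wrong as written for two of its components. For asymptomatic cerebral infarction the observed count will be zero except for chance findings, at any true rate, and reporting it under a definition of absence would present an unassessed event as one that did not occur. For pulmonary vein stenosis the count will be biased low by an amount the documents do not allow one to estimate. The other components and the primary endpoint are not affected.

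The conclusion on silent infarction rests only on the protocol's own schedule and on its statement that no examinations beyond routine care are included. The figures of about 4, 8 and 16 patients in 79 rest on assumed rates of 5%, 10% and 20% with no detection. They illustrate the problem and do not estimate how many patients would be misclassified.

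**What to change.** Change the wording of Section 7 and carry it into the report:

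1. Delete asymptomatic cerebral infarction from the definition of safety.
2. Define the stenosis component as clinically apparent or incidentally detected pulmonary vein stenosis confirmed by imaging, so that a case seen on a study echo still counts. State that stenosis was not systematically screened for.
3. Leave all other components as they are. Several, such as tamponade or vascular injury, may be recognised during the procedure or on examination, so a rule based on imaging would not suit them.
4. List any silent infarct found by chance separately, outside the safety count.
5. State in the report that silent infarction was not assessed. Make no claim of its absence and give no confidence limit from a zero count.

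No added imaging, patients or visits are needed. The cost is a narrower safety claim: the study could speak to clinically apparent complications and to stenosis as it happened to be found, but not to silent brain injury.

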	
Life Survey (AFEQT), with values ranging from 20 - 140 (higher scores mean worse outcomes).
 
Secondary End Points
 
(1) The rate of atrial fibrillation-free recurrence during clinical follow-up within 12 months after surgery, that is, the success rate of pulsed field therapy for AF (including atrial tachycardia (AT) lasting more than 30 seconds, atrial flutter (AFL), and AF endpoint events);
 
(2) Complications and adverse events during the pulsed field ablation surgery and during the postoperative follow-up, including readmission, cardiovascular events, cardiovascular death, all-cause death, and also including serious adverse events related to the surgery.
 
(3) Rehospitalization due to heart failure or recurrence of atrial fibrillation 3 months after surgery;
 
(4) The incidence of AT/AF/AFL events 3 months later.;
 
(5) Improvement of cardiac function 6 and 12 months after surgery, including echocardiogram E/e', proBNP, etc.

Statistical analysis
	
OPC was analyzed based on previous clinical research data and used for comparison and evaluation of the main evaluation indicators. According to the current literature on the treatment of drug-refractory atrial fibrillation, the main evaluation indicator comparison target value was 80%.
 
1. Completion status and demographic analysis
 
Summarize the number of enrollments and completions of each center, and list the list of dropouts. Make a detailed list of the size of different data sets in each group, the distribution of cases in each center, the comparison of the total dropout rate, and the reasons for non-completion. Describe, analyze and evaluate the patient's demographic characteristics (age, gender, etc.), relevant medical history, treatment history, etc.
 
2. Safety evaluation
 
List the number and frequency of all adverse events, as well as the incidence of adverse events and serious adverse events. Make a cross-tabulation description of the changes in laboratory indicators before and after. The exact probability

	method was used to compare the two groups of adverse events.
--	--

Flow chart

Name	Screening period		Treatment period		Follow-up period			
	V1	V2	V3	V4	V5	V6	V7	
Visit point								
Visit time	-14d ~ 0d	0 d (Operation)	1-7 d (Before discharge)	1m ± 7d	3m ± 7d	6m ± 7d	12m ± 7d	
Informed consent	X							
General information	X							
Vital signs	X		X	X	X	X	X	
Medical history	X							
Inclusion criteria	X							

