1、 The AFEQT value of the endpoint of the pulse catheter ablation group be selected from the

CABANA heart failure cohort at 12 months, which is 80.6 (19.8). Referring to the KiCS-AF cohort study, which divided the AFEQT improvement value into three levels of 5, 10 and 15, we set the AFEQT value of the drug treatment group to 75.6/70.6/65.6.

2、 Set the AFEQT of the drug group to 75.6, $\alpha=0.05$, $\beta=0.2$, and 248 patients are required in each group.

Numeric Results for an Unequal-Variance T-Test

$$\delta = \mu_1 - \mu_2$$

Hypotheses: $H_0: \delta = 0$ vs. $H_1: \delta \neq 0$

Target Power	Actual Power	N1	N2	N	μ_1	μ_2	δ	σ_1	σ_2	Alpha
0.8	0.80138	248	248	496	80.6	75.6	5	19.8	19.8	0.05

3、 Set the AFEQT of the drug group to 70.6, $\alpha=0.05$, $\beta=0.2$, and 63 cases are needed in each group. Considering a dropout rate of 20%, 79 cases are needed in each group.

Numeric Results for an Unequal-Variance T-Test

$$\delta = \mu_1 - \mu_2$$

Hypotheses: $H_0: \delta = 0$ vs. $H_1: \delta \neq 0$

Target Power	Actual Power	N1	N2	N	μ_1	μ_2	δ	σ_1	σ_2	Alpha
0.8	0.80306	63	63	126	80.6	70.6	10	19.8	19.8	0.05

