3.7 Criteria and procedures for stopping the trial/trial treatment

The criteria for stopping the study/trial treatment include, but are not limited to:

- (1) The subject withdraws from the trial;
- (2) Unexpected serious adverse events of the device occur, causing serious danger to the subjects participating in the study;
- (3) The medical device regulatory authority or ethics committee requires the trial to be stopped;
- (4) Other circumstances that require the trial/trial treatment to be stopped;

Procedures for Discontinuation of Study/Study Treatment:

- (1) Subjects withdraw from the study: Regardless of the reason, the records of cases withdrawing from the study should be retained, and the last evaluation and examination results should be carried forward as the final results, and the full data set analysis should be conducted on their efficacy and safety. The study conclusions and reasons for the withdrawal of all cases should be recorded;

(2) Ethics Committee requires the study to be stopped: For ethical and scientific reasons, the ethics committee requires the study to be stopped. After the researcher learns of the situation, the researcher should stop the study in a timely manner and keep the communication records or written documents of the study cessation;

(3) Regulatory agency requires the study to be stopped: If the medical device supervision and management department requires the study to be stopped, the person in charge of the study should notify each research unit in writing in a timely manner after learning of the situation;

(4) Other situations where the study/research treatment must be stopped: The situation where the subject stops the study/research treatment due to illness or other reasons should be recorded in detail; the cessation of the entire study should be reported to each research unit in writing in a timely manner; other situations where the study/treatment must be stopped should also be recorded in detail.

4. Study plan

4.1 Treatment of patients in the drug group:

Patients who enter the drug group after screening can receive electrical cardioversion or drug cardioversion for drug treatment. If the patient undergoes electrical cardioversion, preoperative examinations must be completed before surgery to exclude surgical contraindications.

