The blank period starts from the day 0 when the patient receives Class I or Class III antiarrhythmic drugs, and the blank period of the drug group is from Day 0 to the next 90 days. During the blank period, patients can undergo electrical cardioversion to recover to sinus rhythm (if patients have recurrent atrial fibrillation during the blank period, they can choose to undergo electrical cardioversion again without the limit of countless times). Titration and adjustment of antiarrhythmic drugs are allowed during the blank period. In principle, no drug adjustments will be made after the blank period. Increasing the dose of the original Class I or Class III drugs or replacing antiarrhythmic drugs due to intolerance or drug side effects is considered the end point. Adding Class II or Class IV antiarrhythmic drugs for other reasons is allowed.

4.2 Treatment of patients in the surgical group::

4.2.1 Preoperative preparation:

(1) Class II and IV antiarrhythmic drugs, diuretics, digitalis drugs, etc. are allowed before surgery. The purpose is to control ventricular rate and improve heart failure treatment. The researcher can decide whether to continue taking the above-mentioned drugs;

(2) Anticoagulants, including warfarin and new oral anticoagulants, should not be discontinued before surgery. For warfarin, INR should be routinely tested before surgery;

(3) Complete preoperative examinations to exclude surgical contraindications (such as left atrial thrombus, abnormal coagulation function, severe thrombocytopenia, liver dysfunction, acute renal dysfunction, acute heart failure, etc.).

4.2.2 Intraoperative operation:

(1) General anesthesia;

(2) Heparin anticoagulation and maintaining ACT at 250-350 seconds;

(3) Single atrial septal puncture via femoral vein;

(4) Conventional PulseSelect PFA ring catheter preparation: flush the guidewire cavity, then insert the guidewire into the catheter through the guidewire Luer interface, retract the ring electrode into the introducer, slowly push the catheter slide control button forward to make the ring electrode linear, and at the same time push the introducer to retract the ring electrode. PulseSelect PFA ring catheter is inserted into the sheath.

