The following information should be collected/completed at the $6m \pm 15d$ follow-up after surgery:

- ◆ Vital signs
- ◆ Standard electrocardiogram
- ◆ Holter
- ◆ AFEQT quality of life score for patients with atrial fibrillation
- ◆ Cardiac ultrasound
- ◆ Medication status
- ◆ Adverse events & serious adverse events

(7) V8 12 months post-surgery

The following information should be collected/completed at the $12m \pm 15d$ follow-up after surgery:

- ◆ Vital signs
- ◆ Laboratory tests
- ◆ Standard electrocardiogram
- ◆ Holter
- ◆ AFEQT quality of life score for patients with atrial fibrillation
- ◆ Cardiac ultrasound

- ◆ Medication status
- ◆ Adverse events & serious adverse events

Note: Medication status: Record the medication status during the study period (from signing the informed consent to the end of follow-up). Routine solution preparation (normal saline, glucose solution), intraoperative anesthetics, and intraoperative anticoagulants do not need to be recorded. Drugs used for corrective treatment of adverse events also need to be recorded.

Adverse events: Record clinically significant adverse events of the subjects from signing the informed consent to the end of follow-up. Events in which the health status of the subjects does not deteriorate seriously due to planned hospitalization for existing diseases or follow-up required by the protocol are not recorded as serious adverse events.

5. End point

5.1. Primary endpoint:

Change in quality of life at 12 months as measured by the Atrial Fibrillation Quality of Life Survey (AFEQT). Improvement in quality of life from baseline to 12 months after pulsed field ablation procedure or AAD as measured by the Atrial Fibrillation Quality of Life Survey (AFEQT), with values ranging from 20 - 140 (higher scores mean worse outcomes).

5.2 Secondary endpoint:

- (1) The rate of atrial fibrillation-free recurrence during clinical follow-up within 12 months after surgery, that is, the success rate of pulsed field therapy for AF (including atrial tachycardia (AT) lasting more than 30 seconds, atrial flutter (AFL), and AF endpoint events);
- (2) Complications and adverse events during the pulsed field ablation surgery and during the postoperative follow-up, including readmission, cardiovascular events, cardiovascular death, all-cause death, and also including serious adverse events related to the surgery.
- (3) Rehospitalization due to heart failure or recurrence of atrial fibrillation 3 months after surgery;

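### Carrying withdrawn patients' last rhythm result forward and comparing crude proportions understates 12-month AF/AT/AFL recurrence at the planned 20% dropout

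*Protocol*

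**What the plan says.** **Endpoints.** Section 5.2 lists as secondary endpoint (1) "The rate of atrial fibrillation-free recurrence during clinical follow-up within 12 months after surgery", which it equates with the success rate of pulsed field therapy, and as secondary endpoint (4) "The incidence of AT/AF/AFL events 3 months later". Section 2.2, item (2), states that recurrence is to be compared with the drug group.

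**Test.** Section 9, (2) item 5: "The composition ratio is used for statistical description of qualitative data, and the chi-square test is used for statistical inference". The other tests named have other targets. Section 9 gives a t-test for molecular data and a Kruskal-Wallis test for NYHA class. The Study Protocol Summary gives an exact "method was used to compare the two groups of adverse events". Kaplan-Meier, log-rank and Cox appear nowhere.

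**Withdrawals.** Section 3.7, on subjects who withdraw: "the last evaluation and examination results should be carried forward as the final results". The full data set is then analysed for efficacy and safety.

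**Expected losses.** Section 3.1: "Considering a dropout rate of 20%, 79 cases are needed in each group".

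**Timing.** Section 4.1: "the blank period of the drug group is from Day 0 to the next 90 days". Section 6: "Holter is used for follow-up at 3, 6 and 12 months after surgery". Section 6 also schedules ECGs at 1, 3, 6 and 12 months.

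**The concern.** A crude 12-month proportion is sound when every patient's 12-month status is known. The protocol expects about one patient in five to leave, and section 3.7 then supplies the missing status from the last visit. For an outcome that can only move from free to recurred, this works in one direction. A patient who had already recurred stays recurred, and a patient who leaves while free is recorded as free at month 12, even though part of the at-risk period was never observed.

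Two consequences follow. Recurrence is understated in both groups, so the 12-month success rate is too favourable. And the group that loses more patients looks better. Section 3 divides patients into a drug group and a procedure group and describes no randomisation, and the two treatments are visibly different. Unequal dropout is therefore plausible, although the protocol does not predict it.

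**Working it through.** **1. The plan's own figure.** Inputs from section 3.1: difference 10, SD 19.8 in both groups, two-sided alpha 0.05, power 0.80. The unequal-variance t-test has power 0.7967 at 62 per group and 0.8031 at 63, so n = 63. Dropout: 63 / (1 − 0.20) = 78.75, rounded up to 79, or 158 in total. Both stated figures reproduce. The 20% was set for AFEQT, but the same patients supply the rhythm data: 0.20 × 79 ≈ 16 per group.

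**2. Model for recurrence.** The protocol gives no recurrence rate and no dropout by group, so these are assumptions, shown over a range. Time is in years. Recurrence has a constant hazard from b = 0.25 (about 90 days) to 1, and dropout a constant hazard from 0 to 1, independent of recurrence. With true recurrence p and dropout d:

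- λ = −ln(1 − p) / (1 − b)
- γ = −ln(1 − d)
- proportion reported as recurred under carry-forward = exp(−γb) × λ/(λ + γ) × [1 − exp(−(λ + γ)(1 − b))]

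Example, p = 0.40 and d = 0.20: λ = 0.5108/0.75 = 0.6811 and γ = 0.2231. The result is 0.9457 × 0.7532 × 0.4925 = 0.351.

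**3. Size of the understatement at 20% dropout.**

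| True recurrence | Reported under carry-forward | Points too low |
|---|---|---|
| 20% | 17.5% | 2.5 |
| 30% | 26.3% | 3.7 |
| 40% | 35.1% | 4.9 |
| 50% | 44.0% | 6.0 |
| 60% | 52.9% | 7.1 |

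With no blanking window (b = 0), the reported figures run from 18.0% to 54.7%, which is 2.0 to 5.3 points too low.

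**4. Type I error, 79 per group, 20,000 simulated trials per scenario.**

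| Equal true recurrence | Dropout by group | Blanking window | Chi-square with carry-forward | Log-rank |
|---|---|---|---|---|
| 40% | 20% / 20% | yes | about 5% | about 5% |
| 40% | 10% / 30% | yes | 10.4% | 4.9% |
| 50% | 10% / 30% | yes | 11.9% | 4.8% |
| 50% | 10% / 30% | no | about 9% | about 5% |
| 50% | 15% / 25% | no | 5.8% | about 5% |

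In the third row, two groups with the same true recurrence of 50% would on average report 47.0% and 40.7%.

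**5. Power with equal 20% dropout.** At true 30% against 50%: chi-square with carry-forward 65%, log-rank 68%. At 40% against 60%: 62% and 68%.

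**6. Is the test or the carry-forward rule at fault?** Same model, 40% against 60%, no blanking window, chi-square kept. Excluding everyone who leaves before month 12, whether or not they had recurred, gives 40.0% and 59.9%, essentially unbiased, with power of about 62%. Removing only those who leave free of recurrence gives 43.0% and 63.1%, which is too high. The bias comes from how leavers are counted.

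**The case against.** **Chi-square is legitimate here.** Section 5.2 words endpoint (1) as a success rate, which can be read as a binary 12-month outcome, and a chi-square test on that is valid. This stands. A reader might infer that the test itself is wrong, but step 6 shows otherwise: with all early leavers excluded and dropout unrelated to recurrence, the same test gives unbiased rates and keeps its size. The fault is the combination of crude proportions with section 3.7.

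**A separate analysis plan may cover it.** Section 9 assigns chi-square to categorical data in general and does not name recurrence, and endpoint-specific methods are often left to a later plan. This stands in part. But section 3.7 fixes how withdrawals are treated, and it would contradict censoring unless it is expressly disapplied.

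**The false-positive rate depends on a chosen scenario.** This stands. A reader might infer that the comparison will be anti-conservative in any case. With equal dropout the size is near 5%, and at 15% against 25% it was 5.8% in the scenario shown. The 9% to 12% needs a contrast of about 10% against 30%, which the documents do not predict.

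**Time-to-event methods bring their own assumptions.** Also true. Log-rank and Cox need dropout to be non-informative. If patients leave because treatment is failing, they do not remove the bias. Fixed-visit ECG and Holter date only the detection of a recurrence, not its onset.

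**Conclusion.** The point holds in limited form. Followed as written, the protocol understates 12-month recurrence by about 2.5 to 7 percentage points at 20% dropout, for assumed true recurrence of 20% to 60% with a 90-day window. This rests on constant hazards, on dropout unrelated to recurrence, and on the 20% applying to the rhythm endpoints and being handled under section 3.7.

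The effect on the comparison is conditional. A type I error of about 9% to 12% arises with assumed dropout of 10% against 30% and equal true recurrence of 40% to 50%. With equal dropout the test keeps its size and loses only a few points of power. The documents support neither the claim that chi-square is invalid in itself nor the claim that a false difference is to be expected whatever the dropout.

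These are secondary endpoints, and the AFEQT primary endpoint is outside this point. The correction is still worth making before data are analysed, because endpoint (1) is the protocol's measure of ablation success and the error flatters it.

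**What to change.** In section 9, for secondary endpoints (1) and (4):

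- State that the carry-forward rule in section 3.7 does not apply, and cross-refer from section 3.7.
- Estimate 12-month freedom from AF/AT/AFL by Kaplan-Meier, using the date of first detection and censoring at the last rhythm assessment.
- Compare groups by log-rank or a Cox model. If the model is adjusted, name the baseline factors, since the protocol lists none.
- Add an interval-censored sensitivity analysis, because rhythm is checked at fixed visits.
- Report dropout and its reasons by group, with a worst-case sensitivity analysis for patients who leave without recurrence.
- Keep chi-square for categorical outcomes with complete status.

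The start of follow-up and the blanking window also need reconciling. Section 4.1 defines both explicitly for the drug group only, while section 4.3 mentions a 3-month window for both treatments in its recommendations on medication. One time origin and one counting rule should be stated for both groups.

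The cost is small but is more than a change of wording. The case report form must capture the date of first detected recurrence and of the last rhythm assessment, which the protocol does not explicitly require. Sample size and visit schedule are unaffected.
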